5.6. Exploratory Analysis of Effectiveness

Exploratory analyses that were not described in SAP Part A will be included in this section. This section also documents modifications or additions to the analysis plan which are resulted from information that was not available at the time of SAP Part A finalization.

5.6.1. Durability of Vaccine Efficacy of Primary Series (including data from both blinded and OL- Phase before boost Data)

The durability of vaccine efficacy may be evaluated to see if the effect of the vaccine is waning over time. These exploratory analyses will include data from both blinded phase (Part A) and OL-phase (Part B) before booster.

5.6.1.1. Methods Proposed by Tsiatis and Davidian (2021a/b)

Tsiatis and Davidian (2021a/b) proposed a framework to conceptualize counting process for infection by making transparent assumptions about biological, behavioral and other phenomena. The method provides a mechanism based on inverse probability weighting (IPW) to account for possible confounding. The confounding is introduced in the process of unblinding and post-treatment choice of cross-over to vaccine for those who are originally assigned to placebo.

In this approach, the VE is modeled via the following infection rate ratio

$$R^b(\tau; \theta) = \exp\{\zeta(\tau)\}I(\tau < \ell) + \exp\{\theta_0 + g(\tau - \ell; \theta_1)\}I(\tau \geq \ell) \quad (1)$$

and $VE=1-R^b(\tau; \theta)$

Here, τ is the time since vaccination, and ℓ is the lag time from vaccination to full immunity achieved, which is approximately 6 weeks (2 doses given 28 days apart, and 14 days for vaccine effect to ramp up) The relevant VE is therefore estimated by two parts:

- The first part is via θ_0 , which models the VE at the time when full immunity is achieved ($\tau = \ell$). This is mainly estimated via the data from double-blind period where the infection data from both vaccine arm and placebo arm is available.
- The second part is via θ_1 , which models the waning effect as a function of time since vaccination. $\theta_1 = 0$ implies that VE doesn't change with time since vaccination, and $\theta_1 > 0$ implies that VE decreases with increased time since vaccination, meaning waning. And the value of θ_1 indicates the magnitude of waning effect. We will explore different optional form of the g function (e.g. linear, or piece-wise constant) to evaluate how the effect change over time.
 - The data from unblinded phase will contributing in estimating the waning effect θ_1 , by evaluating how infection rates changes under vaccine arm after different times since vaccination τ_1 and τ_2 . The infection rates can be estimated based on the infection status data at time t from vaccinated individuals who received vaccine at times $t - \tau_1$ and $t - \tau_2$, respectively.

This will reflect information about waning of the vaccine itself while controlling for the possibly different background infection rate at time t .

Data will be censored at the time of booster.

A sensitivity analysis may be performed including the stratification factor (≥ 18 and < 65 years and not at risk, ≥ 18 and < 65 years and at risk, or ≥ 65 years) as covariates for building models for entry, unblinding and censoring mechanism to evaluate the impact of confounding.

5.6.1.2. Methods Proposed by Lin et al (2021, 2022)

Lin et al (2021, 2022) proposed a method to evaluate long-term COVID-19 vaccine efficacy using Cox regression model with a time-varying vaccine effect

$$\lambda(t|S, X) = \lambda_0(t)e^{(\beta X + I(t > S)\eta(t-S))} \quad (2)$$

Where $\eta(t - S)$ is a piece-wise linear function (e.g. every week).

Here, S denote the time when first dose of vaccination takes place and T denote the time when the endpoint events occurs. Both times are measured in days from the start of the clinical trial. We measure each participant's time to disease from the start of the trial rather than from their time of enrollment because the risk of disease depends on community transmission, which varies over the calendar time. The two timescales are different under staggered enrollment. X denote baseline stratification factor (≥ 18 and < 65 years and not at risk, ≥ 18 and < 65 years and at risk, or ≥ 65 years).

Based on the cox regression, vaccine effect is modeled as a function (η) of time since vaccination ($t-S$) while controlling for the possibly different background infection rate at time t . We may evaluate both the cumulative vaccine effect over the time and instantaneous vaccine effect over time.

5.6.2. The effectiveness of booster

It is important to note that since the variant circulating in the community is changing over time, so the time effect could be partially confounded with boost effect if the infection rate before and post boost is compared without adjustment. To handle this issue, the cox model with time-varying covariates allows the comparison of boosted vs un-boosted at any given time t time, and this adjustment estimate the boost effect while controlling for the possibly different background infection ratio at time t . In all analysis below, we will analyze the infection caused by any variant. Variant-specific analysis for booster may be explored using competing risk framework (i.e. censoring the other variant which is not of the primary interest) in the future. These analyses may be applied to assess effectiveness of booster on COVID-19, severe COVID-19 and death due to COVID-19.

Specifically, two approaches may be used for exploratory analysis to evaluate the effectiveness of booster.

5.6.2.1 Methods Proposed by Lin et al (2021, 2022)

The effectiveness of booster will be analyzed by a modification of Cox regression model with a time-varying vaccine effect proposed by Lin et al (2021, 2022). The hazard function is modeled by:

$$\lambda(t|S, X) = \lambda_0(t)e^{(\beta X + I(t>S)\eta(t-S))} \quad (3)$$

Where S is the calendar time of boost, and t is the calendar time of the infection. So $\eta(t-S)$ is a piece-wise linear function (e.g. every week) which models the booster effect over time as a function of time since boost. It will also provide information on when the booster achieves its full effect.

The data will only include the subject who had completed the full primary series (two doses of mRNA-1273 vaccine, PP Set). And the time will start at the time when the first subject received the 2nd dose of mRNA-1273 (time zero). Each of the subject will enter

the risk set at the time they took the 2nd dose. To control the waning effect of the prime, time of 2nd dose from time zero will be included as a covariate in X. X also include the baseline stratification factor for randomization.

5.6.2.2 Methods Proposed by Fintzi and Follmann (2021)

Another exploratory analysis to evaluate the effectiveness of booster is using cox proportional hazard model with booster as a time-varying covariate (Fintzi and Follmann 2021, also known as step-wedge approach) . Such model compares the infection rate for boosted vs unboosted at a given time t. Time since second dose of vaccination will be included as a continuous covariate. This can be viewed as an analysis of an individual level step-wedge observational study (Brown and Lilford 2006). It is similar to the analyses used to assess booster efficacy of the BNT162b2 vaccine in Israel [Bar-On et al 2021]. Technically, we will use the following model with t as calendar time:

$$h(t) = h_0(t) \exp(b_1 * ZB(t) + b_2 * TPS + b_3 * ZB(t) * TPS + b_4 * X_1 + b_5 * X_2) \quad (4)$$

Here, ZB(t) is the time-varying covariate which takes value of 0 before boost, and takes the value of 1, 14 or more days after boost. Since the booster effect may not be fully achieved until 14-days after the injection, subjects and their events (if any) during the 14-day period will be removed from the risk set between the boost dose date and 14 days later. X1 and X2 are covariates coded for stratification factor (≥ 18 and < 65 years and not at risk, ≥ 18 and < 65 years and at risk, or ≥ 65 years).

If we define TP as the time since second dose as of the earliest date of a participant receiving the booster (first date of fist booster dose), TPS is the standardized time since prime defined as $TP - \min(TP)$. $\min(TP)$ is the time since prime for the subject who had the shortest time since prime. This standardization (via subtraction) is to facilitate the interpretation of the parameter estimation.

In this case, boost efficacy by standardized time since prime can be estimated as

$$BE(tps) = 1 - \exp(b1 + b3 tps)$$

where BE at $tps=0$ is the boost efficacy among those who had the shortest time since prime.

The analysis will be confined within the period between the time when the first subject with booster administered and the last subject with booster administered. However, it should be noted that since there is no randomization between boosted and unboosted at a given time t , therefore, boost effect will still be confounded with the potential population difference between those who choose to have booster early vs late. So the results should be interpreted with caution. Sensitivity analysis may be considered to adjust for this confounding effect.

A sensitivity analysis about the impact of time since prime will use a binary variable instead of a continuous covariate. This binary variable will indicate if the subject received vaccine as original randomized treatment (early cohort), or as the cross-over treatment after unblinding when vaccine is approved (late cohort). Another form of sensitivity analysis will include quadratic function of TPS.

It is important to note that since the booster effect reflect the average effect 14 or more days after booster. If the full effect is not achieved by day 14, then this average effect will be smaller than the full effect. This result will be interpreted together with the results from model (3).

Additional exploratory analysis may be performed to assess the impact of covariates in addition to the stratification factor for randomization (age and risk group) that could potentially associated with booster time and COVID risk, such as time since prime, sex, race/ethnicity, or occupational risk.

6 Changes from Planned Analyses in Protocol

Not applicable.

7 References

Estimands and Sensitivity Analysis in Clinical Trials. The Guideline on Statistical Principles for Clinical Trials. International Council for Harmonisation (ICH) E9(R1). November 2019.


8 List of Appendices

Appendix A Standards for Variable Display in TFLs

Continuous Variables: The precision for continuous variables will be based on the precision of the data itself. The mean and median will be presented to one more significant figure than the original results; the SD will be presented to two more significant figures than the original results; the minimum and maximum will be presented to the same precision as the original results.

Categorical Variables: Percentages will be presented to 1 decimal place. If the count is 0, the percentage will not be displayed. If the count equals the denominator, the percentage will be displayed as 100.

Appendix B Analysis Visit Windows

Analysis will be summarized using the following analysis visit window for post injection assessments:

Step 1: If the assessments are collected at a scheduled visit, the collected data will be mapped to the nominal scheduled visit.

Step 2: If the assessments are collected at an unscheduled visit, the collected data will be mapped using the analysis visit windows described in Table B-1 below. For subjects with confirmed COVID-19, unscheduled assessments will be preferably mapped to the visits with respect to the confirmation of COVID-19 (i.e. Illness Visit Day xx) over nominal scheduled visits (i.e. Day xx).

If a subject has multiple assessments within the same analysis visit, the following rule will be used:

- If multiple assessments occur within a given analysis visit, the assessment closest to the target study day will be used.
- If there are 2 or more assessments equal distance to the target study day, the last assessment will be used.

Table B-1 Analysis Visit Windows

Visit	Target Study Day	Visit Window in Study Day
NP swab (or saliva)		
Day 1	1 (Date of First Injection)	1, first-dose
Day 29	29 (Date of Second Injection)	
Illness Visit Day 1	X (Date of NP Swab test)	X
Illness Visit Day 3	X+2	[X+1, X+2]

Illness Visit Day 5	X+4	[X+3, X+4]
Illness Visit Day 7	X+6	[X+5, X+6]
Illness Visit Day 9	X+8	[X+7, X+10]
Illness Visit Day 14	X+13	[X+11, X+16]
Illness Visit Day 21	X+20	[X+17, X+23]
Illness Visit Day 28	X+27	[X+24, X+34]
PDV	Y	Y
BD Day 1	Z	Z
Vital Signs		
Day 1	1 (Date of First Injection)	1, Pre-first-dose
Day 1	1 (Date of First Injection)	1, Post-first-dose
Day 29	29 (Date of Second Injection)	[2, 43] Pre-second-dose
Day 29	29 (Date of Second Injection)	[2, 43] Post-second-dose
Day 57	57	[44, 133]
Day 209	209	[134, 301]
Day 394	394	[302, 576]
Day 759	759	[577, end of study if did not receive booster]
Illness Visit Day 1	X (Date of COVID-19 Confirmation)	X
Illness Visit Day 28	X+27	[X+2, X+34]
OL Day 1	Y (Date of First Injection in Part B)	Y, Pre-first-dose in Part B

OL Day 1	Y (Date of First Injection in Part B)	Y, Post-first-dose in Part B
OL Day 29	Y+28 (Date of Second Injection in Part B)	[Y+1, Y+42], Pre-second-dose in Part B
OL Day 29	Y+28 (Date of Second Injection in Part B)	[Y+1, Y+42], Post-second-dose in Part B
OL Day 57	Y+56	[Y+43, Y+70]
BD Day 1	Z (Date of Booster Dose in Part C)	Z, Pre-first-dose in Part C
BD Day 1	Z (Date of Booster Dose in Part C)	Z, Post-first-dose in Part C
BD Day 29	Z+28	[Z+1, Z+105]
BD Day 181	Z+180	[Z+106, end of study if received booster]
Immunogenicity		
Day 1	1	1, first-dose
Day 29	29 (Date of Second Injection)	[2, 43] Pre-second-dose
Day 57	57	[44, 133]
Day 209	209	[134, 301]
Day 394	394	[302, 576]
Day 759	759	[577, end of study if did not receive booster]
Illness Visit Day 1	X (Date of NP Swab test)	X
Illness Visit Day 28	X+27	[X+2, X+34]

OL Day 1	Y (Date of First Injection in Part B)	Y, first-dose in Part B
OL Day 29	Y+28 (Date of Second Injection in Part B)	[Y+1, Y+42], second-dose in Part B, for participants who will receive 1 dose in Part B
OL Day 57	Y+56	[Y+1, Y+70], for participants who will receive 2 doses in Part B
BD Day 1	Z (Date of Booster Dose in Part C)	Z, Pre-first-dose in Part C
BD Day 29	Z+28	[Z+1, Z+105]
BD Day 181	Z+180	[Z+106, end of study if received booster]

Appendix C Imputation Rules for Missing Dates of Prior/Concomitant Medications and Non-Study Vaccinations

Imputation rules for missing or partial start/stop dates of medication are defined below:

1. Missing or partial medication start date:
 - If only Day is missing, use the first day of the month, unless:
 - The medication end date is on/after the date of first injection or is missing/partial AND the start month and year of the medication coincide with the start month and year of the first injection. In this case, use the date of first injection.
 - If Day and Month are both missing, use the first day of the year, unless:
 - The medication end date is on/after the date of first injection or is missing/partial AND the start year of the medication coincide with the start year of the first injection. In this case, use the date of first injection.
 - If Day, Month, and Year are all missing, the date will not be imputed, but the medication will be treated as though it began prior to the first injection for purposes of determining if status as prior or concomitant.
2. Missing or partial medication stop date:
 - a. If only Day is missing, use the earliest date of (last day of the month, study completion, discontinuation from the study, or death).
 - b. If Day and Month are both missing, use the earliest date of (last day of the year, study completion, discontinuation from the study, or death).
 - c. If Day, Month, and Year are all missing, the date will not be imputed, but the medication will be flagged as a continuing medication.

In summary, the prior, concomitant or post categorization of medications and non-study vaccinations is described in the table below.

Table C-1 Concomitant, and Post Categorization of Medications and Non-study Vaccinations

Part B			
Medication Start Date	Medication Stop Date		
	< First Injection Date of mRNA-1273 in the open-label phase	≥ First Injection Date in the open-label phase and ≤ 28 Days After Last Injection in the open-label phase	> 28 Days After Last Injection in the open-label phase [2]
< First injection date of mRNA-1273 in the open-label phase [1]	-	C	C, A
≥ First injection date in the open-label phase and ≤ 28 days after last injection in the open-label phase	-	C	C, A
> 28 days after last injection in the open-label phase	-	-	A
Part C			
Medication Start Date	Medication Stop Date		

	< Injection Date of mRNA-1273 in the booster dose phase	≥ Injection Date in the booster dose phase and ≤ 28 Days After Injection in the booster dose phase	> 28 Days After Injection in the booster dose phase [2]
< Injection date of mRNA-1273 in the booster dose phase [1]	-	C	C, A
≥ Injection date in the booster dose phase and ≤ 28 days after injection in the booster dose phase	-	C	C, A
> 28 days after injection in the booster dose phase	-	-	A

A: Post; C: Concomitant; P: Prior

[1] includes medications with completely missing start date

[2] includes medications with completely missing end date

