6.3. Study Treatment Compliance

All doses of IP will be administered at the study site under direct observation of unblinded medically qualified study personnel and appropriately recorded (date and time) in the eCRF. Unblinded personnel will confirm that the participant has received the entire dose of vaccine. If a participant does not receive vaccine or does not receive all of the planned doses, the reason for the missed dose will be recorded. Data will be reconciled with site accountability records to assess compliance.

Participants who miss the second dose of IP due to noncompliance with the visit schedule and not due to a safety pause will still be required to follow the original visit and testing schedule as described in the protocol. Except for participants who withdraw consent or who are withdrawn from the study due to receipt of non-study COVID-19 primary series or first booster vaccine ([Section 7.3.1](#)), a participant who withdraws or is withheld from receiving the second dose of study vaccine in Part A or Part B will remain in the study and complete all efficacy, safety, and immunogenicity assessments required through the participant's scheduled end of study.

The study site is responsible for ensuring that participants comply with the study windows allowed. If a participant misses a visit, every effort should be made to contact the participant and complete a visit within the defined visit window ([SoE Tables](#), [Section 11.1](#)). If a participant does not complete a visit within the time window, that visit will be classified as a missed visit (with the

exception of Dose 2 visits in Part A and Part B, as applicable) and the participant will continue with subsequent scheduled study visits. All safety requirements of the missed visit will be captured and included in the subsequent visit (eg, clinical laboratory testing, eDiary review for reactogenicity, immunologic testing, as applicable).

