8.2.6. Blood Sampling

The maximum planned volumes of blood sampled for immunogenicity analyses per participant are approximately 50 mL for 1 day, 100 mL for 28 days ([Table 16](#)), and 300 to 420 mL (dependent on participation in Part B and Part C) for the total study volume ([Table 4](#)).

Table 4: Maximum Planned Immunogenicity Blood Sampling Volumes per Participant by Visit

Study Visit Day	Table 16 D1	Table 16 D29	Table 16 D57	Table 17 D209	Table 17 D394	Table 18 D759	Total
Immunogenicity blood samples ^a	50 mL	50 mL	50 mL	50 mL	50 mL	50 mL	300 mL
Study Visit Day	Part B Day 1^b	Part B Day 29^b	Part B Day 57^b	NA	NA	NA	NA
Immunogenicity blood samples ^a	20 mL	20 mL	20 mL	NA	NA	NA	60 mL ^c
Study Visit Day	Part C Day 1^d	Part C Day 4^d	Part C Day 29^d	Part C Day 181^d	NA	NA	NA
Immunogenicity blood samples ^a	24 mL	8 mL	24 mL	24 mL	NA	NA	80 mL

Abbreviations: COVID-19 = coronavirus disease 2019; D = Day; NA = not applicable; RT-PCR = reverse transcriptase polymerase chain reaction; OL = open-label; SoE = schedule of events.

^a Additional blood samples (16 mL) will be taken at Illness Day 1 and Convalescent Visit Day 28 for those participants who report symptoms of COVID-19 and who have RT-PCR confirmed symptomatic COVID-19, respectively.

^b If a visit from SoE [Table 16](#) and [Table 17](#) and a Part B visit overlap, only the Part B sample will be taken (using the Part B kit). The exception would be if an Illness Day 1 or Convalescent Visit Day 28 overlapped with a Part B visit. In this case the Illness and Convalescent Visit Day 28 samples would be taken and the corresponding kits used.

- ^c For participants who received placebo during the Part A Blinded Phase and receive mRNA-1273 during Part B. Note that immunogenicity blood samples are collected only on OL-D1 and OL-D57 (Table 21) or OL-D1 and OL-D29 (Table 22) in Part B.
- ^d If a visit from SoE Table 17 and Table 18 and a Part C visit overlap, only the Part C sample will be taken (using the Part C kit). Exceptions would be if an Illness Day 1 or Convalescent Visit Day 28 overlapped with a Part C visit, in this case the Illness and Convalescent Visit Day 28 samples would be taken and corresponding kits used, or in the case of a Part C Day 4 visit, both sets of samples would need to be taken using both kits.

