5.5.3.2. Immunobridging of response of a Booster as compared to Primary Series

Immunobridging analyses of a booster as compared to the primary series will be performed using the neutralizing antibody titers (as measured by PsVNA) 28 days following the booster dose (BD-D29) to the corresponding titers 28 days following the second dose of the primary series (Day 57 of the blinded phase for the mRNA-1273 cohort).

Immunobridging analyses may also be performed using binding antibody specific to S-protein by MSD.

The following endpoints will be used for this analysis:

- Geometric mean titer (GMT)
- Seroreponse Rate (SRR)

For GMT:

In the situation that subjects in PPIS-Neg Set have the same specific nAb (e.g. PsVNA) at baseline/pre-Dose 1, 28 days after Dose 2 of primary series, pre-booster, 28 days after booster and other timepoints, GMT ratios will be calculated by back transforming the mean of within-subject paired differences of antibody titers on the logarithmic scale between post-booster Day 29 (of the booster phase) and Day 57 of primary series (Day 57 of the blinded phase for the mRNA-1273 cohort). CIs for the GMT ratio will be based on t-distribution of the log-transformed values then back transformed to the original scale for presentation.

Another approach is to compare the post-booster antibody titers in Part C with the post-primary series titers in baseline-SARS-CoV-2 negative mRNA-1273 participants. An analysis of covariance (ANCOVA) model will be performed using the Part C PPIS-Neg Set with baseline-SARS-CoV-2 negative mRNA-1273 participants in PPSI (considering as historical control). In the model, antibody titers at 28 days post-booster (BD-Day 29) and post-Dose 2 of primary series will be a dependent variable, and a group variable (Booster and mRNA-1273 primary series) will be the fixed effect, adjusting for age groups (< 65, ≥ 65 years). The GMT will be estimated by the geometric least square mean (GLSM) from the model and its corresponding 95% CI will be provided for each group. The GMR (ratio of GMTs) for Booster with respect to mRNA-1273 primary series will be estimated by the ratio of GLSM from the model and the corresponding 95% CI will be provided. The 95% CI for

GMR will be used to assess the between group difference in immune response 28 days post-booster as compared to 28 days post-Dose 2 of the primary series.

For Seroresponse:

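### The OL Day 57 and BD-Day 29 immunogenicity windows can admit a titer drawn before open-label Dose 2 or far from 28 days after the booster, when the scheduled visit is missed or late

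*SAP*

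**What the plan says.** The mapping rules are in Appendix B of the SAP for Parts B and C.

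- Step 1: "If the assessments are collected at a scheduled visit, the collected data will be mapped to the nominal scheduled visit". No date limit is attached.
- Step 2: "If the assessments are collected at an unscheduled visit, the collected data will be mapped using the analysis visit windows" of Table B-1. For participants with confirmed COVID-19, unscheduled samples go preferably to the Illness Visit rows.
- Several samples in one window: "the assessment closest to the target study day will be used".

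The relevant Table B-1 rows, with Y the date of open-label Dose 1 and Z the date of the booster, are:

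- OL Day 57, immunogenicity: target Y+56, window "Y+1, Y+70], for participants who will receive 2 doses in Part B".
- OL Day 57, vital signs: target Y+56, window Y+43 to Y+70.
- BD Day 29, immunogenicity: target Z+28, window Z+1 to Z+105.
- Day 57 of the blinded phase, immunogenicity: target study day 57, window study days 44 to 133.

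Section 5.5.3.2 of the same SAP bases the booster comparison on "neutralizing antibody titers (as measured by PsVNA) 28 days following the booster dose (BD-D29") against titers 28 days after Dose 2 of the primary series. The criteria are a lower 95% confidence bound of at least 0.67 for the GMR and above -10% for the SRR difference.

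The protocol schedules allow -3/+14 days for BD-2 (Table 23) and OL-D57 (Table 21), and -3/+7 days for Day 57 (Table 16). Protocol section 6.3 says of a visit not completed in its window that "that visit will be classified as a missed visit".

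**The concern.** OL Day 57 and BD-Day 29 are both meant to capture the response 28 days after the last dose. The OL Day 57 immunogenicity row opens the day after open-label Dose 1 and carries no post-Dose-2 condition, so it can label a one-dose titer as the response to the full series. Protocol section 2.2.2 reports that neutralizing antibody in the Phase 1 study was marginal after one injection and rose substantially after the second, so such a value would be misleading. The vital-signs row for the same visit does not have this problem, and the two rows disagree without explanation.

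BD-Day 29 feeds the two Part C key secondary endpoints. Its window runs from one day after the booster to fifteen weeks after it, and Step 1 puts no limit on a sample that carries the BD-2 label. A titer taken before the booster response has developed, or after it has declined, could stand for the 28-day value in a formal noninferiority test.

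**Working it through.** **Targets.** Day 57 minus Day 29 = 28 days. (Y+56) minus (Y+28) = 28 days. Z+28 is 28 days after the booster. The targets are consistent with the endpoint.

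**Where the edges come from.** Most edges follow the midpoint between neighbouring visits:
- (29+57)/2 = 43 and (57+209)/2 = 133, matching the Day 57 window of 44 to 133.
- (28+180)/2 = 104, against the stated BD edge of 105, one day off.
- (28+56)/2 = 42, matching the OL Day 57 vital-signs window that opens at Y+43. The immunogenicity row, opening at Y+1, does not follow the rule.

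**OL Day 57.** The window has 70 days. Days strictly before Dose 2:
- Dose 2 at Y+28 (nominal): 27/70 = 39%.
- Dose 2 at Y+25 and Y+42 (the -3/+14 allowance for OL-D29): 24/70 = 34% and 41/70 = 59%.
- With the vital-signs window (28 days wide), no admissible day precedes Dose 2 if Dose 2 is at Y+42 or earlier.

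**BD-Day 29.** Analysis window: 105 days, from -27 to +77 days around target. Protocol visit: 28-3 = 25 to 28+14 = 42, so Z+25 to Z+42, 18 days. Admissible days outside the protocol visit: 105-18 = 87, and 87/105 = 83%.

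**Blinded Day 57, the comparator.** The per-protocol Dose 2 interval of 21 to 42 days puts Dose 2 on study days 22 to 43. The window then admits from 44-43 = 1 to 133-22 = 111 days after Dose 2. The protocol visit is Dose 2 +25 to +35.

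**Who enters the comparison.** The primary population is Part C PPIS-Neg (section 5.5), a subset of Part C PPIS, which section 4.3 limits to participants randomized to mRNA-1273 in Part A. The GMT comparator is blinded Day 57 of that cohort. For SRR, section 5.5.3.2 also names OL-D57 for the Placebo-mRNA-1273 cohort, which PPIS-Neg cannot contain. OL Day 57 remains relevant to the primary-series immunogenicity analyses of the Placebo-mRNA-1273 cohort (Table 1 in section 5.1.5; section 5.5.2).

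**Possible size on the booster side (assumption; no titer kinetics or counts of missed visits are given).** If a share f of booster values is k-fold too low, the GMR is multiplied by k^(-f):
- f = 1%: 0.993 (k = 2) to 0.962 (k = 50).
- f = 5%: 0.966 (k = 2) to 0.822 (k = 50).

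Each mistimed sample can change at most one participant's seroresponse, so the same shares move the booster SRR by at most 1 to 5 percentage points against a margin of 10. For scale, protocol section 4.3 cites a post-booster response in Study P201 of 1.7 times the primary-series peak in this trial. At a GMR of 1.7, the worst case above gives 1.7 × 0.822 = 1.40 as a point estimate, still well above 0.67, although low outliers would also widen the interval.

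**The case against.** The strongest reply is that this is an edge case. The windows apply only to unscheduled samples, and the closest-to-target rule prefers a timely sample whenever one exists. That is correct and confines the exposure to missed or late visits. It does not cover the late sample labelled BD-2, which Step 1 accepts without limit.

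A reader might infer that pre-Dose-2 titers contaminate the booster noninferiority test. They do not reach the GMT comparison, and they reach SRR only through the OL-D57 wording that conflicts with the PPIS definition.

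A reader might also infer that the Day 57 comparator is as exposed as BD-Day 29, given its 1 to 111 days. Section 6.7.1 of the Part A SAP, however, makes only participants with serum at Day 1 and Day 57 eligible for the Random Subcohort, from which PPRSI and PPIS descend. On a natural reading, every member already has a Day 57 sample.

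The source of stray samples is also uncertain. Protocol section 8.2.6 says "Additional blood samples (16 mL) will be taken at Illness Day 1 and Convalescent Visit Day 28", and the first of these draws needs only reported symptoms. Yet section 8.1.2 describes illness blood as being for potential future assessment, and no section plans neutralization testing of PCR-negative illness draws. Table B-1 has an Illness Visit Day 1 immunogenicity row tied to the swab date, so the destination of such draws is ambiguous rather than settled. The optional BD-D4 draw is a scheduled biomarker sample and is not a source.

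Protocol section 6.3 is a site-compliance rule, and it carries immunologic testing from a missed visit to the next one. Step 1 therefore leaves a gap but does not contradict the protocol.

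Finally, wide gap-free windows are ordinary, and the OL Day 57 row is wide because two-dose participants have no OL-D29 blood draw (Table 4, footnote c). That explains the width. It does not explain the absence of a post-Dose-2 condition.

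**Conclusion.** Two defects in wording stand, of minor to moderate weight.

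1. OL Day 57 immunogenicity lacks a post-Dose-2 condition and conflicts with the vital-signs row. It affects the primary-series summaries of the Placebo-mRNA-1273 cohort.
2. When no timely BD-2 sample exists, BD-Day 29 can take a titer from anywhere in Z+1 to Z+105, or a BD-2-labelled sample of any date, into the noninferiority comparison.

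It would be tempting to say that the windows could produce a false finding of noninferiority. The documents do not support that. With Day 57 largely secured by the sampling rule, an early post-booster titer lowers only the booster side, and so does a late one. The latter assumes that titers wane and that no infection intervened. Both work against the booster.

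The number of participants affected is not given, so the 0.993 to 0.822 range for the GMR multiplier is illustrative only.

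**What to change.** - In Table B-1, require OL Day 57 immunogenicity samples to fall after open-label Dose 2. Dose 2 +25 to +42 uses the protocol's own allowance; the minimum is the vital-signs window, Y+43 to Y+70. Anchoring on Dose 2 is preferable, because with Dose 2 at Y+42 the Y+70 limit falls only 28 days after it.
- For the Part C GMT and SRR comparison, use BD-Day 29 samples within Z+25 to Z+42, whether scheduled or unscheduled. At minimum, prespecify a sensitivity analysis restricted to the protocol visit windows (BD-Day 29 = Z+25 to Z+42; Day 57 = Dose 2 +25 to +35).
- Leave the Part A Day 57 mapping unchanged in the main analysis, since those results are already in the clinical study report of 03 August 2021.
- Reconcile the OL-D57 wording for SRR in section 5.5.3.2 with the PPIS definition in section 4.3.

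The cost is a change to SAP wording and a re-mapping of existing data. No new samples are needed. Some out-of-window samples are dropped from the restricted estimate, with some loss of precision; how many cannot be read from the documents, so the count should be reported alongside the result.
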